**Table 3: Questionnaires**

Visit	Age Groups				
	Adult	Teen (ages 12-18)	Caregiver-Teen (ages 12-18)	Pediatric (ages 8-11.9)	Caregiver-Pediatric (ages 6-11.9)
Screening	Clarke	Clarke	n/a	n/a	Clarke
Visit 2	WHO-5 EQ-5D T1DDS DTSQs Hypoglycemia Confidence Scale HABS PSQI IDSS (T1) SUS	WHO-5 EQ-5D PAID-Teen Hypoglycemia Confidence Scale PSQI SUS	WHO-5 P-PAID-Teen Hypoglycemia Confidence Scale PSQI DTSQs IDSS (T1)	EQ-5D-Y PAID-Child	WHO-5 P-PAID-Child Hypoglycemia Confidence Scale PSQI DTSQs IDSS (T1) SUS
Final Visit/Early Withdrawal	WHO-5 EQ-5D T1DDS DTSQc Hypoglycemia Confidence Scale HABS PSQI IDSS (T1) SUS INSPIRE-Adult Clarke HF Questionnaire	WHO-5 EQ-5D PAID-Teen Hypoglycemia Confidence Scale PSQI SUS INSPIRE-Youth Clarke HF Questionnaire	WHO-5 P-PAID-Teen Hypoglycemia Confidence Scale PSQI DTSQc IDSS (T1) INSPIRE-Parent	EQ-5D-Y PAID-Child INSPIRE-Youth	WHO-5 P-PAID-Child Hypoglycemia Confidence Scale PSQI DTSQc IDSS (T1) SUS INSPIRE-Parent Clarke HF Questionnaire

## 6 OBJECTIVES AND ENDPOINTS

### 6.1 Safety Objective

The safety objective of this study is to evaluate the safety of the Omnipod Horizon™ System in patients with type 1 diabetes.

#### 6.1.1 Primary Safety Endpoint

Proportion of subjects with serious device-related adverse events.

#### 6.1.2 Secondary Safety Endpoints

- Proportion of subjects with severe hypoglycemia during hybrid closed-loop
- Proportion of subjects with diabetic ketoacidosis (DKA) during hybrid closed-loop

### 6.2 Primary Effectiveness Objective

The primary effectiveness objective of this study is to evaluate the effectiveness of the Omnipod Horizon™ System.

#### 6.2.1 Primary Effectiveness Endpoint

Percentage of time in range (70-180 mg/dL) during hybrid closed-loop compared to standard therapy for:

- Target BG challenge days (approximately hybrid closed-loop days 1-9)
- Non-challenge days (approximately hybrid closed-loop days 10-14)
- Overall (hybrid closed-loop days 1-14)

### 6.3 Secondary Effectiveness Objective

To evaluate additional glycemic measures of effectiveness of the Omnipod Horizon™ System in patients with type 1 diabetes.

#### 6.3.1 Secondary Effectiveness Endpoints

The secondary objective will be evaluated using the following per subject endpoints:

- Glucose metrics from system CGM during the hybrid closed-loop phase will be compared to the standard therapy phase during the day, overnight, and overall:
  - Mean glucose
  - % of time in range 70-180 mg/dL
  - % of time in range 70-140 mg/dL
  - % of time > 180 mg/dL

- % of time  $\geq$  250 mg/dL
- % of time  $\geq$  300 mg/dL
- % of time  $<$  70 mg/dL
- % of time  $<$  54 mg/dL
- Standard deviation
- Coefficient of variation

- GMI based on overall mean glucose
- Percentage of time in hybrid closed-loop as proportion of overall device usage time
- Insulin requirements during the hybrid closed-loop phase will be compared to the standard therapy phase:
  - Total daily insulin (TDI) (units, units/kg)
  - Total daily basal insulin (units, units/kg)
  - Total daily bolus insulin (units, units/kg)

## 7 SCREENING AND ELIGIBILITY

Potential subjects for this study will include individuals who have been diagnosed with type 1 diabetes for at least 6 months and are appropriate for pump therapy per investigator's assessment. Potential subjects will be selected at each clinical study site and screened accordingly. Clinical study sites will be advised to:

- Recruit subjects using insulin aspart, lispro, and glulisine also known as Humalog, Novolog, Admelog, and Apidra
- Recruit at least 20% of subjects using MDI

Every effort will be made to establish eligibility of the patient prior to enrollment. Only patients who appear to meet all eligibility criteria will be enrolled in the study. Subject eligibility will be confirmed by study staff during a screening visit at the clinical site. Blood draws will be collected as required to demonstrate study eligibility as noted below. Laboratory results within the last 6 months, with the exception of A1C, may also be used if available.

Subjects that have participated in the prepivotal study may be eligible to extend their participation into the pivotal study.

### 7.1 Visit 1

Visit 1 will be conducted in person at the clinical study site. This visit will assess eligibility and will include:

- Signing of informed consent/assent
- Review of inclusion/exclusion criteria
- Screening assessments performed following Table 2: Schedule of Assessments
- Enrollment

## **Informed Consent/Accent**

Subjects who appear to meet the eligibility criteria will be asked to sign an Informed Consent Form (ICF) approved by each respective Institutional Review Board (IRB) for participation in the study. A parent/guardian must sign the ICF for subjects <18 years of age. Assent will also be obtained from subjects aged <18 years per State requirements. Failure to provide informed consent/assent will render the subject ineligible for the study.

Subjects must also have a signed HIPAA (Health Insurance Portability and Accountability Act) release of protected health information (PHI). The release may be a stand-alone document or part of the informed consent.

After informed consent/assent is obtained, a subject identification number will be issued to uniquely identify each subject. The unique identifier will be used to identify the subject throughout the study and will be used for all source documents and electronic Case Report Forms (eCRFs). Subjects will retain the same subject identification number if they continue in the pivotal study.

## **Inclusion Criteria**

Subjects must meet all of the following criteria in order to be enrolled in the study:

1. Age at time of consent 6-70 years
2. Subjects aged < 18 years must be living with parent/legal guardian
3. Diagnosed with type 1 diabetes for at least 6 months. Diagnosis is based on investigator's clinical judgment
4. Deemed appropriate for pump therapy per investigators assessment taking into account previous history of severe hypoglycemic and hyperglycemic events, and other comorbidities
5. Investigator has confidence that the subject can successfully operate all study devices and is capable of adhering to the protocol
6. Willing to use only Humalog, Novolog, Admelog or Apidra during the study
7. Must be willing to set target glucose between 130-150 mg/dL each for approximately 72-hours on predefined days during the hybrid closed-loop phase
8. Must be willing to extend their participation into the pivotal study if they continue to meet the protocol criteria
9. Willing to wear the system continuously throughout the study
10. A1C <10% at screening visit
11. Must be willing to use the Dexcom App on the Omnipod Horizon PDM as the sole source of Dexcom data (with the exception of the Dexcom Follow App) during the hybrid closed-loop phase
12. Subjects scoring  $\geq 4$  on the Clarke Questionnaire must agree to have an overnight companion, defined as someone who resides in the same home or building as the study subject and who can be available overnight
13. Able to read and speak English fluently
14. Subject must be in an AT&T covered area
15. Willing and able to sign the Informed Consent Form (ICF) and/or has a parent/guardian willing and able to sign the ICF. Assent will be obtained from

subjects aged < 18 years per State requirements.

### **Exclusion Criteria**

Subjects who meet any of the following criteria will be excluded from the study:

1. A medical condition, which in the opinion of the investigator, would put the subject at an unacceptable safety risk
2. History of severe hypoglycemia (as defined in Section 11.3.3) in the past 6 months
3. History of Diabetic Ketoacidosis (DKA) (as defined in Section 11.3.4) in the past 6 months, unrelated to an intercurrent illness, infusion set failure or initial diagnosis
4. Diagnosed with sickle cell disease
5. Diagnosed with hemophilia or any other bleeding disorders
6. Plans to receive blood transfusion over the course of the study
7. Currently diagnosed with anorexia nervosa or bulimia
8. Acute or chronic kidney disease (e.g. estimated GFR < 45) or currently on hemodialysis
9. History of adrenal insufficiency
10. Has taken oral or injectable steroids within the past 8 weeks or plans to take oral or injectable steroids during the course of the study
11. Unable to tolerate adhesive tape or has any unresolved skin condition in the area of sensor or pump placement
12. Use of insulin other than U-100 insulin intended for use in the pump
13. Use of non-insulin anti-diabetic medication other than metformin (e.g. GLP1 agonist, SGLT2 inhibitor, DPP-4 inhibitor, pramlintide)
14. Current or known history of coronary artery disease that is not stable with medical management, including unstable angina, or angina that prevents moderate exercise despite medical management, or a history of myocardial infarction, percutaneous coronary intervention, or coronary artery bypass grafting within the previous 12 months.
15. For subjects > 50 years old or with diabetes duration > 20 years, abnormal electrocardiogram consistent with increased risk of arrhythmia, ischemia, or prolonged QTc interval (> 450 ms)
16. Thyroid Stimulating Hormone (TSH) is outside of normal range with clinical signs of hypothyroidism or hyperthyroidism
17. Pregnant or lactating, or is a woman of childbearing potential and not on acceptable form of birth control (acceptable includes abstinence, condoms, oral/injectable contraceptives, IUD or implant)
18. Participation in another clinical study using an investigational drug or device within the preceding 30-days or intends to participate during the study period
19. Unable to follow clinical protocol for the duration of the study or is otherwise deemed unacceptable to participate in the study per the investigator's clinical judgment

### **Screening Assessments**

Subjects who have signed the informed consent and appear to meet the eligibility criteria will continue to the screening assessments which will be performed at the clinical study site.

Screening assessments must be completed within 30-days prior to the start date of the hybrid closed-loop phase (assessments do not need to be completed on the same day) and include the following:

- Medical history (including prior and current medical conditions and surgical history)
- Demographics (age, gender, race)
- A1C\*
- Thyroid Stimulating Hormone (TSH) level (local laboratory)
- Creatinine level (local laboratory)
- Pregnancy test for women of childbearing potential
- Review of concomitant medications
- Height
- Weight
- Assessment of vital signs
- Electrocardiogram (if applicable, see exclusion criteria 15)
- Questionnaire (Table 3: Questionnaires):
  - Clarke
    - Used to assess impaired awareness of hypoglycemia
- For Dexcom G6 users, assessment of whether subjects have met the CGM usage and data criteria to participate in an abbreviated standard therapy phase (Visit 2 only) per Table 2: Schedule of Assessments
  - At least 80% CGM use (11.2-days) during any consecutive 14-days in the past 30-days and
  - $\geq 2,016$  CGM values during the 14-days

\*Clinical sites will send the blood specimens for A1C to a NGSP (National Glycohemoglobin Standardization Program) certified central laboratory. A point of care (POC) A1C may be used to determine eligibility.

The Clarke Questionnaire will be administered during the screening visit. Subjects scoring  $\geq 4$  on the Clarke Questionnaire will require an overnight companion during the hybrid closed-loop phase. A companion is defined as someone who resides in the same home or building as the study subject and who can be available overnight.

## **Enrollment**

Subjects who meet all eligibility criteria and have completed all screening assessments will continue to enrollment. A subject is enrolled in the study upon placement of the first study CGM. Subjects that do not meet the eligibility criteria will not continue in the study and will be considered screen failures.

If for any reason a subject is no longer eligible for the study after the standard therapy phase has commenced but prior to the commencement of the hybrid closed-loop phase, the subject will not continue in the prepivot study. No additional study assessments will be required. The reason for study exit will be clearly documented.

## 8 STANDARD THERAPY - PHASE 1

The standard therapy phase will commence after all standard therapy assessments are completed per **Visit 2** – see Table 2: Schedule of Assessments.

During the standard therapy phase, subjects will be asked to perform the following:

- Manage their diabetes at home per their usual routine
- Administer meal boluses per their usual dosing routine
- Change their sensor if a sensor fails, or as needed
- Calibrate their CGM, if required, per the manufacturer's instructions
- Monitor their capillary blood glucose (BG) per usual routine
- Give meal boluses. The timing of the bolus delivery will be per each subject's typical dosing routine.

Extending standard therapy past 14-days will not constitute a protocol deviation unless standard therapy extends past 30-days. If subjects extend beyond the 14-days, the most recent 14-days of data will be used in the endpoint analysis if the data meets the criteria defined for CGM use and data availability. If a subject enrolls into the pivotal study, data collected in the standard therapy phase will be used in the endpoint analyses for the pivotal study as the subject will not be required to repeat the standard therapy phase as part of the pivotal study.

The standard therapy phase will be customized depending on the following subject profile:

- Current Dexcom G6 users
- Non-G6 users
- Pump Naïve users

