**Group 2:**

2. N=20 subjects aged 6-70 years will participate in the hybrid closed-loop phase in a remotely monitored 14-day outpatient environment
  - N=10 subjects aged 6-13.9 years
  - N=10 subjects aged 14-70 years

The first group of subjects (n=16) will commence the hybrid closed-loop phase in the hotel setting. On study day 3, subjects will transition to the outpatient setting for the remaining 12-days. After all subjects from the first group have completed the 2-day hotel phase, the second group of subjects may commence hybrid closed-loop. The second group of subjects (n=20) will use hybrid closed-loop in the outpatient setting for 14-days. It is anticipated that Group 1 will solely consist of existing Dexcom G6 users (those who were using the Dexcom G6 at the time of screening), while Group 2 will include some existing Dexcom G6 users and some non-Dexcom G6 users. Therefore, the primary safety and primary effectiveness endpoints will also be presented by Dexcom G6 use (users and non-users).

[figure not shown]
All subjects will participate in target BG challenges during the hybrid closed-loop phase. In total, all subjects will complete 14-days of closed-loop control, with approximately 72-hours spent at target blood glucose levels set to 130mg/dL, 140mg/dL and 150mg/dL, respectively.

After each subject in the prepivotal study has successfully completed 14-days of hybrid-closed-loop, they may immediately transition to and enroll in the pivotal study bypassing standard therapy (Phase 1) and continuing with the pivotal hybrid closed-loop phase (Phase 2). Remote monitoring will be discontinued as each subject enrolls in the pivotal study.

After 16-subjects from the prepivotal study have completed a minimum of 10-days on hybrid-closed-loop, the Data Safety Monitoring Board (DSMB) will convene and if the system is determined to be safe, the pivotal study may open enrollment to additional subjects for the hybrid closed-loop phase (Phase 2).

The standard therapy phase (Phase 1) of the pivotal study may commence in parallel to the prepivotal study. Figure 3 is a representation of the prepivotal transition into pivotal.

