### Current Dexcom G6 Users

Current Dexcom G6 users will be required to participate in the assessments required as part of standard therapy but may be exempt from wearing the study CGM for 14-days if the following criteria are met:

- Willing to provide 14-days of CGM data from the past 30-days
- Meet the success criteria of 80% CGM use during any consecutive 14-days in the past 30-days
- Must have  $\geq 2,016$  CGM values during the 14-days

If exemption criteria are not met, subjects may choose to continue to collect data until they meet the criteria or will be required to participate in the entire 14-day standard therapy phase consistent with the requirements for non-G6 users.

Subjects deemed exempt from wearing the study CGM for 14-days will be eligible to immediately commence the hybrid closed-loop phase.

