#### **8.1 Visit 2**

**Visit 2** represents the commencement of the standard therapy phase. All scheduled assessments will be performed according to Table 2: Schedule of Assessments. This visit will include:

- Review of concomitant medications
- Average total daily insulin (approximately over the past 7 days)
- Average total daily basal insulin (approximately over the past 7 days)
- Average total daily bolus insulin (approximately over the past 7 days)
- Review pump settings/MDI dosing
- Completion of questionnaires (see Table 3: Questionnaires for specific requirements by age group):
  - WHO-5
    - Used to measure current mental well-being
  - EQ-5D
    - Used to measure quality of life
  - T1DDS
    - Used to measure four critical dimensions of distress
  - DTSQs
    - Used to measure satisfaction with diabetes treatment regimens
  - Hypoglycemia Confidence Scale
    - Used to measure hypoglycemia unawareness, hypoglycemia frequency, severity and impact
  - HABS
    - Used to measure critical dimensions of hypoglycemia related concerns and confidence
  - PSQI
    - Used to measure sleep disturbance and usual sleep habits
  - IDSS (T1)
    - Used to measure patient satisfaction with their devices and impact on quality of life
  - SUS

- Used to measure usability of a system
- PAID-(Teen, Child)
  - Measures diabetes-related burden
- Training on Glucagon administration and information on treatment of hypo/hyperglycemia
  - All subjects are required to have access to glucagon and receive training on how to deliver the medication
- Study device training per manufacturer's instructions (CGM - blinded, BG, and ketone meters)
- Dispensing of CGM (blinded for non-G6 users), BG, and ketone meter
- QC testing of BG and ketone meter
  - Must pass at least one level of quality control testing prior to dispensing
- CGM sensor placement (if applicable)
  - Approved anatomical locations for CGM sensor placement will be reinforced as well as the importance of using approved locations

During this visit, subjects will be dispensed the following supplies:

- Dexcom transmitter
- Dexcom receiver
- Dexcom sensors
- Contour® Next One blood glucose meter
- Contour® Next One blood glucose meter test strips
- Contour® Next One blood glucose meter control solution
- Lancets
- Precision Xtra blood ketone meter
- Precision Xtra blood ketone meter test strips
- Precision Xtra blood ketone meter control solution

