### **11.3.2 Reportable Adverse Events**

Adverse events will be assessed on an ongoing basis throughout the study. Adverse event reporting will begin at the start time of the standard therapy phase (i.e., insertion of the CGM sensor) and continue through the hybrid closed-loop phase until the subject's participation has ended. All adverse events must be followed until resolution, or until the AE has stabilized, or until the study has been completed.

Pre-existing medical conditions or symptoms observed prior to the start time of the standard therapy phase will not be recorded as an AE and should be collected in the subject's medical history. In the event there is a change (i.e., worsening) in the pre-existing medical condition or symptoms after enrollment meeting the criteria of a reportable adverse event, then an AE must be reported.

For this protocol, a reportable adverse event includes any untoward medical occurrence that meets one of the following criteria:

1. An SAE
2. An ADE unless excluded from reporting in Hypoglycemic Events and Hyperglycemic/Ketotic Events sections below
3. An AE occurring in association with a study procedure
4. An AE not related to a study device issue which leads to temporary or permanent discontinuation of the study device
5. An AE that affects the participant's ability to complete any study procedures
6. An AE for which a visit is made to a hospital emergency department
7. Hypoglycemic Events as defined below
8. Hyperglycemic/Ketotic Events as defined below.

Skin reactions from sensor or pod placement are only reportable if severe and/or required treatment.

For the purpose of this protocol, mild symptoms of hypoglycemia and hyperglycemia (i.e., clinically non-significant) or blood glucose values out of the normal range (whether or not they resulted in delayed meals or correction boluses) will not be reported as AEs unless determined to meet the reportable criteria in the Hypoglycemic Events and Hyperglycemic/Ketotic Events sections below.

All reportable AEs—whether volunteered by the participant, discovered by study personnel during questioning, or detected through physical examination, laboratory test, or other means—will be reported on an AE eCRF.

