### 12.3.1 ITT (Intention to Treat) Analysis Set

The ITT analysis set includes all subjects that are enrolled in the study. All safety analyses (other than primary analysis of primary safety endpoints) will be based on the ITT analysis set.

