### 5.4 ANALYSIS OF ADVERSE EVENTS

Safety summaries and analyses will be based on all subjects that are enrolled in the study (i.e., Intention to Treat analysis set). All adverse events reported over the course of the study will be summarized and tabulated by study phase (standard therapy or HCL), event category, seriousness, severity, and relationship to the study procedures and the investigational device. Except where indicated, a subject reporting the same adverse event more than once will be counted once when calculating the number and percentage of subjects with that particular event. Adverse Event outcomes will be assessed descriptively as opposed to inferentially.

Adverse events leading to death or to discontinuation from the study will be listed separately. A listing of all adverse events will be provided. No formal tests of hypotheses are proposed for the safety endpoints.

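### Enrollment is tied to first study CGM placement, which exempt Dexcom G6 users may not reach until closed-loop start, so exits and adverse events before closed-loop can be counted differently by prior G6 use

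*Protocol*

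**What the plan says.** **Enrollment and ITT.** Protocol 7.1 (Enrollment) and SAP 2.7 use the same trigger: "A subject is enrolled in the study upon placement of the first study CGM". Both reserve the term screen failure for subjects who do not meet eligibility. Protocol 12.3.1 then says: "The ITT analysis set includes all subjects that are enrolled in the study". SAP 5.4 adds: "Safety summaries and analyses will be based on all subjects that are enrolled in the study", with adverse events "tabulated by study phase (standard therapy or HCL), event category, seriousness, severity". Baseline tables also cover all enrolled subjects (Protocol 12.7, SAP 7.6).

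**Exempt G6 users.** Section 8 says that current G6 users "may be exempt from wearing the study CGM for 14-days if the following criteria are met". Their standard therapy is abbreviated to Visit 2 (7.1, Screening Assessments), and they may skip Visit 3 (Table 2 footnotes). In 8.1, sensor placement at Visit 2 is conditional on its being applicable. Non-G6 users must do the whole 14-day phase wearing a blinded study CGM.

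**Start of the phase and of reporting.** Section 8.1 says that Visit 2 "represents the commencement of the standard therapy phase", and the opening of Section 8 agrees. Section 11.3.2 reads differently: "Adverse event reporting will begin at the start time of the standard therapy phase (i.e., insertion of the CGM sensor" (its parenthesis closes there).

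**Who is likely to be a G6 user.** Section 5.2: "It is anticipated that Group 1 will solely consist of existing Dexcom G6 users". Group 2 is expected to be mixed.

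**The concern.** The trigger for enrollment is an event that one kind of subject has at Visit 2 and another kind may not have until closed-loop start. Both kinds go through Visit 2, with its questionnaires, device training and, for MDI users, advice on insulin before closed-loop. Pump-naive subjects may also wear a saline-filled Pod during this phase.

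If the rules are applied as written, two things follow. The count of subjects lost before closed-loop can omit exempt users. The standard-therapy adverse event table can be less complete for exempt users than for non-G6 users. A reader who compares the two phases, or looks at attrition, would then see a difference that comes partly from the definition and is aligned with prior G6 use.

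**Working it through.** No power or event-rate formula applies: the sample size is not hypothesis-driven and the documents state no figure for this point. The check is to trace the definitions for two subjects with the same history, and then to bound the size.

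**1. Definitions side by side**

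| Situation | Non-G6 user | Exempt G6 user with no study sensor at Visit 2 |
|---|---|---|
| Completes Visit 2 | Enrolled at sensor placement | Not yet enrolled |
| Eligible, leaves before closed-loop | In ITT | Not in ITT, and not a screen failure |
| Event in the interval, 11.3.2 read as sensor insertion | Reportable if criteria met | Not reportable |
| Event in the interval, 11.3.2 read as Visit 2 | Reportable if criteria met | Reportable if criteria met, but in ITT tables only if later enrolled |
| Enters closed-loop with a study sensor | In ITT and mITT | In ITT and mITT |

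There are thus two separate mechanisms. Rows 1 and 2 follow from the enrollment definition. Row 3 follows from the parenthesis in 11.3.2 and applies even to an exempt user who later enters ITT. Section 11.3.2 also sends conditions observed before the start time to medical history.

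**2. Does another passage settle it?** The SAP prevails over the protocol (SAP 1), but SAP 2.7 repeats the same trigger. Protocol 7.1 lists enrollment among the Visit 1 activities, which is a third version. The lists for Visits 2 and 3 (8.1, 8.2) contain no adverse event assessment; the Visit 4 list (9.3) does. The adverse event row of Table 2, as its columns read in the extracted text, also begins at Visit 4. No passage gives exempt users another enrollment point.

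**3. Size**

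- Planned evaluable subjects: 18 + 18 = 36 by age, and 16 + 20 = 36 by group.
- Group 1 share: 16/36 = 44%. This counts anticipated G6 users, not exempt ones.
- Interval: the Table 2 window for Visit 2 runs from 14 days before closed-loop to closed-loop start, so 0 to 14 days per exempt subject.
- Standard-therapy adverse event proportion: suppose k of 36 subjects are exempt with no reportable time, event rates are otherwise equal, and all 36 stay in the denominator. The proportion is multiplied by (36 − k)/36. For k = 0 the factor is 1. For k = 16 it is 20/36 = 0.56. For k = 30 it is 6/36 = 0.17. These k are assumptions. Part of this dilution would remain under any trigger, because standard therapy is short by design for exempt users.
- Disposition: suppose 48 subjects complete Visit 2 and d exempt users leave before a study sensor is placed. ITT is then 48 − d: 47 for d = 1 and 42 for d = 6. These d are also assumptions; the documents give no dropout rate.

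**The case against.** The strongest reply is that little follows from the wording, and much of that reply stands.

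- **Endpoints.** SAP 7.1.2 makes mITT the primary set for all primary and secondary endpoints, and SAP 3.1 counts the safety endpoints during closed-loop. A reader might infer bias in those results; the documents do not support that.
- **Events and ITT.** A reader might infer that all events after Visit 2 in exempt users fall outside ITT. They do not: an exempt user who reaches closed-loop with a study sensor is in ITT. Section 11.3.2 also does not specify a *study* sensor, and Sections 8 and 8.1 support a Visit 2 start. The defect there is an ambiguity, not an established exclusion.
- **Recording.** A reader might infer that these exits and events are simply lost. Table 2 provides an early withdrawal visit for subjects who started but did not finish, and 9.9 includes adverse event assessment and the reason for withdrawal. Section 7.1 requires the exit reason when eligibility is lost, and 11.3.2 lists procedure-associated events as reportable. Information may well be recorded, but it has no assigned place in the ITT tables.
- **Timing of placement.** CGM supplies are dispensed at Visit 2 without an exception for G6 users, and the exemption could be read as waiving only the 14-day duration. Late placement is therefore possible, not shown.
- **Scale.** A reader might multiply 16 × 14 = 224 subject-days for Group 1. That needs all 16 to be exempt, none to have a sensor at Visit 2, and every Visit 2 to fall a full 14 days early, although exempt users may start closed-loop at once. Nor does Group 2's wait for the hotel stays necessarily lengthen the interval, since the Visit 2 window is counted back from each subject's own closed-loop start.

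What remains is that the written rules place two eligible subjects with the same history differently, and that the start of adverse event reporting is given in conflicting ways.

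**Conclusion.** The concern holds, with minor consequence. As written, an eligible exempt G6 user who leaves after Visit 2 and before a study sensor is placed belongs to no category, while the matching non-G6 user is in ITT. Separately, whether an exempt user's events in that interval are reportable depends on which of two conflicting statements is followed.

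The effect reaches only the standard-therapy adverse event tables, the all-enrolled baseline tables and disposition before closed-loop. Its size cannot be fixed from the documents: the number of exempt users is not given, and the effect is nil if every exempt user has a study sensor placed at Visit 2 or starts closed-loop that day. The conclusion assumes that some exempt users have neither, which 8.1 and Table 2 permit.

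**What to change.** 1. In Protocol 7.1 and SAP 2.7, define enrollment as completion of the Visit 2 assessments, or first study CGM placement if that is earlier.
2. In Protocol 11.3.2, start adverse event reporting at that same point for every subject, exempt or not, and remove the parenthesis about sensor insertion.
3. Bring the Visit 1 enrollment item in 7.1, the phase start in Sections 8 and 8.1, and the adverse event row of Table 2 into line with it.

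The cost is a few sentences and one table row. The ITT set, the count toward the limit of 48 and the number of reported events may each grow slightly. No endpoint analysis has to change.
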